### 3.2.4 Patient Disposition and Demographics

Demographic, baseline characteristics will be summarized in FAS. Demographic including age, gender, ethnicity, race, region, Familial Partial Lipodystrophy (FPL) Group as entered on the Randomization CRF will be summarized using descriptive statistics. In addition, FPL Group derived based on the data entered on the Disease History CRF and the genetic testing results as below will be summarized.

- Patients with a pathogenic mutation in known FPL genes according to the University of Chicago data (for patients who consented to genetic testing) or historical genetic testing results (for patients who did not consent) will be assigned to Group 1.
  - Patients who do not belong in Group 1 and have a family history of FPL or a similar fat distribution and/or history of fat loss in a first degree relative, plus at least 1 minor criterion as entered in the Disease History CRF will be assigned to Group 2. Minor criteria refers to protocol section 5.1 inclusion criteria.
  - Patients who do not belong in Group 1 or Group 2 and have at least 2 minor criteria as entered in the Disease History CRF and a Screening BMI  $< 35 \text{ kg/m}^2$  will be assigned to Group 3.
  - Patients who do not fall into one of the categories above will be assigned to None.

Baseline characteristics includes: body weight, height at screening, BMI, fasting lipids results including

Baseline data will be listed for all randomized patients.

All screened patients will be included in the summary of patient disposition. The number of patients screened, randomized, dosed, number of patients included in each analysis set, completed treatment, discontinued treatment along with reasons for discontinuing treatment, entered post-treatment follow-up, completed post-treatment follow-up, and discontinued post-treatment follow-up along with reasons for early terminating post-treatment follow-up, will be presented for both randomized treatment period and OLE period by treatment group to which they were randomized, and overall.

Listing of patient disposition will also be provided for all randomized patients.

Medical history will be coded by Medical Dictionary for Regulatory Activities (MedDRA) dictionary Version 19.1 and will be summarized by system organ class and preferred term by treatment and overall for the SAF1 . Medical history will also be provided in the data listings.

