#### **3.3.2 Analysis of Primary Endpoint**

The primary efficacy analysis will be the comparison of the percent change from Baseline to Randomized Treatment Period Month 3 in fasting triglyceride between volanesorsen group and placebo group in the FAS. The data will be analyzed using an analysis of covariance (ANCOVA) model with the randomization stratification factor (diagnosis of disease with or without genetics and family history) derived based on the Disease History CRF and genetic testing results and treatment group as factors and baseline fasting triglyceride as a covariate. In the ANCOVA model, triglyceride will be log-transformed. Patients with a missing primary endpoint will be excluded from primary efficacy analysis.

The primary efficacy analysis model (ANCOVA) will be repeated for the percent change from baseline in fasting triglyceride at Randomized Treatment Period endpoint month 6 and month 12.

A subgroup analysis of the primary efficacy analysis model (ANCOVA) will also be conducted in the group of genetically confirmed patients according to the University of Chicago data for patients who consented to genetic testing or historical data for patients who did not consent, and for patients with no mutation at month 3, month 6 and month 12. An interaction term of treatment group by derived FPL group will be included as a factor in the ANCOVA model.

The sample SAS code for the ANCOVA model can be found below:

```
*****
* Note: Base = Baseline fasting triglyceride *
*      LOGBASE = Log-transformed baseline fasting triglyceride *
*      PCHG = Percent change from Baseline at Month 3 *
*      TRTP = Treatment group: Placebo, volanesorsen *
*      FPLGRPD = Derived FPL groups: 1 = FPL1, 2 = FPL2, 3=FPL3 *
*      FPL1 - Phenotype + Genetic Variants *
*      FPL2 - Phenotype + No Genetic Variant + Family Hist or Abnormal and *
```

\* Similar Fat + 1 Minor Criterion \*  
\* FPL3 - Phenotype + No Genetic Variant + No Family Hist or Abnormal and \*  
\* Similar Fat + 2 Minor Criteria + BMI<35kg/m2 \*  
\* \*  
\*\*\*\*\*

```
ods output lsmeans=lsm diff=diff;  
proc mixed data = M3TG;  
  class TRTP (ref='Placebo') FPLGRPD;  
  model PCHG = TRTP FPLGRPD LOGBASE /solution cl residual outp=predresid;  
  lsmeans TRTP/e diff cl;  
run;
```

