### ***3.4.2 Analysis of Secondary Endpoints***

#### ***3.4.2.1 Secondary Endpoint 1: Percent Change from Baseline in hepatic steatosis (as assessed by hepatic fat fraction using magnetic resonance imaging [MRI])***

Hepatic fat fraction (%), change from baseline, and percent change from baseline will be summarized by analysis visit using descriptive statistics in FAS. They will also be summarized separately by genetic mutation category: LMNA+PPARG, or neither. Descriptive summary statistics refers to section 3.2.1. Visit includes baseline and analysis visits according to the visit window defined in [Appendix B](#).

The percent change in Hepatic Fat Fraction (%) from Baseline to month 6 and month 12 at Randomized Treatment Period will be analyzed using the similar ANCOVA model as for the primary efficacy analysis model (ANCOVA).

A subgroup analysis of the ANCOVA will also be run for percent change in hepatic fat fraction in the group of genetically confirmed patients according to the University of Chicago data for patients who consented to genetic testing or historical data for patients who did not consent, and in patients with no mutation at month 6 and month 12 respectively.

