#### ***3.4.2.2 Secondary Endpoint 2: Change from Baseline in HbA1c***

HbA1c (%), change from baseline, and percent change from baseline will be summarized by analysis visit using descriptive statistics in FAS. They will also be summarized separately by genetic mutation category: LMNA, PPARG, or neither. Descriptive summary statistics refers to section 3.2.1. Visit includes baseline and analysis visits according to the visit window defined in [Appendix B](#).

The change in HbA1c from Baseline to Randomized Treatment Period month 3, month 6, month 9 and month 12 will be analyzed using this similar ANCOVA model as for the primary efficacy analysis

A subgroup analysis of the ANCOVA will also be run for change in HbA1c from baseline in the group of genetically confirmed patients according to the University of Chicago data for patients who consented to genetic testing or historical data for patients who did not consent, and in patients with no mutation at month 3, month 6, month 9 and month 12 respectively.

**3.4.2.3 Secondary Endpoint 3: Proportion of patients who achieve a >=40% reduction in fasting triglyceride from Baseline and >=30% reduction of hepatic fat fraction percent from baseline at Month 6**

Frequency and proportion of patients who achieve a >=40% reduction in fasting triglyceride from baseline and >=30% reduction of hepatic fat fraction from baseline at Month 6 will be displayed.

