### **3.8 Changes in the Planned Analysis**

Study treatment is discontinued before completing the protocol specified treatment period. The following protocol specified analysis will not be conducted at the final analysis.

1. Protocol section 10.3 “Per Protocol Set (PPS)”, in final analysis, Per Protocol Set will not be classified. All analysis endpoint will not be assessed in PPS.
2. Protocol section 10.6.3 primary efficacy analysis, patient with missing primary endpoint will be excluded from primary efficacy analysis (ANCOVA). Protocol specified imputation method and sensitivity analysis to assess the robustness of the primary analysis results will not be conducted. For secondary efficacy analysis (patients who achieve a  $\geq 40\%$  reduction in fasting triglyceride from Baseline and  $\geq 30\%$  reduction of hepatic fat fraction percent from baseline at Month 6), protocol specified statistical comparison will not be conducted, only descriptive summary will be provided. The change from baseline in fasting triglycerides, hepatic fat fraction, and HbA1c will be assessed using ANCOVA model with derived FPL based off of genetic confirmation as a stratification factor. A subset analysis will look at the change from baseline in fasting triglycerides, hepatic fat fraction, and HbA1c by gene mutation of LMNA + PPARG and no mutation. The ANOCOVA model used for this analysis will include an interaction term between treatment and FPL group
3. Protocol section 10.1.2 states that Disease burden score is one of secondary efficacy endpoint. However this patient-reported outcome is not collected in the study. Disease burden score will not be summarized.

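### The genetic subgroup ANCOVA adds a treatment-by-FPL-group interaction without saying where it is fitted, specifies no test by mutation status, and defines its subset in two conflicting ways

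*SAP*

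**What the plan says.** **Subgroup and interaction.** SAP 3.3.2 plans a subgroup ANCOVA "conducted in the group of genetically confirmed patients according to the University of Chicago data for patients who consented to genetic testing", or by historical data for those who did not consent, and also for patients with no mutation. It then adds: "An interaction term of treatment group by derived FPL group will be included as a factor in the ANCOVA model". The sample code below it lists treatment, derived FPL group and log baseline only. SAP 3.8 repeats the interaction between treatment and FPL group for the subset analyses of TG, hepatic fat fraction (HFF) and HbA1c.

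**Derived FPL group.** SAP 3.2.4 builds Group 1 from "Patients with a pathogenic mutation in known FPL genes according to the University of Chicago data" for consenting patients, "or historical genetic testing results (for patients who did not consent) will be assigned to Group 1". Groups 2 and 3 are drawn from patients who are not in Group 1. A fourth level exists: "Patients who do not fall into one of the categories above will be assigned to None". The three-level list in the sample code omits it.

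**Genetic categories.**
- Subgroup ANCOVA in 3.3.2 (TG), 3.4.2.1 (HFF) and 3.4.2.2 (HbA1c): genetically confirmed versus no mutation.
- Subset ANCOVA in 3.8, all three endpoints: "by gene mutation of LMNA + PPARG and no mutation". The Version 2.0 entry in the SAP's Summary of Changes agrees with 3.8, but the conflict rests on 3.8 itself.
- Descriptive HFF summary in 3.4.2.1: "They will also be summarized separately by genetic mutation category: LMNA+PPARG, or neither".
- Descriptive HbA1c summary in 3.4.2.2: "They will also be summarized separately by genetic mutation category: LMNA, PPARG, or neither".

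**The concern.** An interaction in a subgroup analysis normally serves to ask whether the treatment effect differs between the subgroups. Here the interacting factor is FPL group, not mutation status, and the subsets are themselves cut by the rule that defines FPL group. Depending on where the model is run, the term is empty, answers a family-history question, or is a three-group test that nobody has translated into a mutation contrast. Two programmers could follow the text and produce different tables.

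The two subset definitions add to this. Protocol 5.1 gives AKT2, CIDEC and PLIN1, beside LMNA and PPAR-γ, as examples of qualifying genes. A carrier of one of these three is genetically confirmed under 3.3.2. Under 3.8 the same patient is neither LMNA + PPARG nor without a mutation, so belongs to no category.

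At stake is the reading of an added subgroup analysis in a small trial. The primary comparison does not use this term.

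**Working it through.** **1. Degrees of freedom for the interaction.** The df equal the rank of the design with the interaction minus the rank without it. With both arms present in every group this is (2 − 1) × (groups present − 1). The design has an intercept, treatment, derived FPL group and log baseline. Ranks were checked on an illustrative data set of 40 patients (20, 10 and 10 in Groups 1, 2 and 3).

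| Data set | Groups present | Rank without | Rank with | df | What the term compares |
|---|---|---|---|---|---|
| Genetically confirmed | 1 | 3 | 3 | 0 | nothing |
| No mutation | 2, 3 | 4 | 5 | 1 | Group 2 with Group 3 |
| FAS | 1, 2, 3 | 5 | 7 | 2 | any difference among three groups |

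The first row follows because 3.3.2 and 3.2.4 use the same two data sources. LMNA and PPARG carriers are also all Group 1, so the 3.8 version gives 0 df in that subset too.

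In the FAS fit, write δ1, δ2, δ3 for the treatment differences by group. A mutation contrast is δ1 − [w·δ2 + (1 − w)·δ3]. The SAP names neither this contrast nor the weight w.

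If 'None' patients are kept as a fourth level in both arms, the FAS term has (2 − 1) × (4 − 1) = 3 df. If they occur in one arm only, that cell is empty and the overall LS-mean treatment difference from the interaction model is not estimable.

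**2. Is the effect in confirmed patients lost?** No. In the illustrative Group 1 subset the treatment difference was −66.83 with and without the redundant term.

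**3. Is the term inert in the no-mutation set?** No. Take, as an assumed illustration, 4 patients in Group 2 with a true effect of −20 and 16 in Group 3 with −60, split evenly by arm. The main-effects model weights by information: (4 × −20 + 16 × −60)/20 = −52. With the interaction, default LS means weight the groups equally: (−20 − 60)/2 = −40.

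**4. Precision of a mutation interaction for TG.** The SAP gives no figure for this. SAP 3.3.3 supplies the SD of 40 points. Its own power statement (20 per arm, difference 40, about 80%) recomputes to Φ(40/(40·√(2/20)) − 1.96) = Φ(1.20) = 88.5%, or 86.9% by the t distribution. That gap is on the conservative side and has no bearing here.

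With 1:1 allocation and mutation-positive share s, the number per arm is N·s/2 in carriers and N·(1 − s)/2 in the rest. Each SE is 40·√(2/n per arm), and the interaction SE is the root of the sum of squares. The difference detectable with 80% power is 2.80 × SE. The share s is not in the documents, so 30%, 50% and 70% are assumed.

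| N | s | SE, carriers | SE, others | SE, interaction | Detectable |
|---|---|---|---|---|---|
| 40 | 30% | 23.1 | 15.1 | 27.6 | 77 |
| 40 | 50% | 17.9 | 17.9 | 25.3 | 71 |
| 40 | 70% | 15.1 | 23.1 | 27.6 | 77 |
| 60 | 30% | 18.9 | 12.3 | 22.5 | 63 |
| 60 | 50% | 14.6 | 14.6 | 20.7 | 58 |
| 60 | 70% | 12.3 | 18.9 | 22.5 | 63 |

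Power for a 40-point effect within carriers alone is 35% to 72% at N = 40 and 51% to 89% at N = 60.

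**The case against.** A reader might infer three stronger claims. The documents do not support them.

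- **That the interaction cannot be estimated.** This holds only for a fit inside the confirmed subset. Neither 3.3.2 nor 3.8 excludes a single FAS fit, where the term has 2 df. Mutation status is nested in derived FPL group, so that fit could also supply a mutation contrast. This stands; what remains is that the SAP specifies neither the data set nor the contrast.
- **That the subgroup question goes unanswered.** SAP 3.3.2 asks for effects in confirmed patients and in patients with no mutation, and both can be produced. The empty term does not alter the first. This stands too. Only the test of a difference between the two is unspecified.
- **That the subgroup is defined three or four ways, so the TG, HFF and HbA1c models describe different patients.** The ANCOVA text is the same for all three endpoints in 3.3.2, 3.4.2.1 and 3.4.2.2. The LMNA/PPARG splits in 3.4.2.1 and 3.4.2.2 are descriptive, and the second can be read as a finer cut of the first. Only 3.8 competes with the ANCOVA definition.

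It can also be said that SAP 1.3 attaches no hypothesis to mutation status and that the test would be weak. Both are true, and both argue for an exploratory label rather than for leaving the model ambiguous. Finally, carriers of other genes may be few or absent: Protocol 2.1 describes 5 reported patients with PLIN1, 4 members of one family with AKT2 and 1 patient with CIDEC mutations. The documents give no count for this trial.

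**Conclusion.** The point holds as a specification fault in the subgroup analysis. Within the two subsets the stated interaction is either empty (0 df) or aimed at Group 2 versus Group 3 (1 df). In the FAS it is estimable (2 df), but no contrast by mutation status is named. Two definitions of the ANCOVA subset conflict, and a carrier of an FPL gene other than LMNA or PPARG is placed under one and nowhere under the other. The primary analysis and the treatment difference in confirmed patients are untouched.

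The 0 df result assumes that genetically confirmed in 3.3.2 means the pathogenic-mutation rule of 3.2.4. The shared data sources support this, but SAP 2.2 counts likely pathogenic variants as positive for stratification while 3.2.4 names pathogenic ones only, so the boundary needs stating. The precision figures rest on SD 40, 40 to 60 patients and the assumed 30% to 70% share.

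**What to change.** - Use one classification, pathogenic FPL variant yes/no, for the TG, HFF and HbA1c subgroup ANCOVAs, and align 3.8 with it. State how likely pathogenic variants and untested patients are classed.
- Fit one model in the FAS, labelled exploratory: treatment, derived FPL group as a main effect, treatment by mutation status (1 df), and the endpoint's own baseline. Keeping FPL group preserves the planned stratification factor and carries the mutation main effect.
- Report the treatment difference within each mutation level, and the interaction, with 95% CIs. Because mutation status is nested in FPL group, request these as explicit contrasts rather than from marginal LS means.
- Add the term to the sample code and say how 'None' patients enter the model.
- Gene-level descriptive summaries may stay, with the same category labels for HFF and HbA1c.

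The cost is SAP wording and one model statement, with no new data. The downside is an imprecise interaction: at 40 to 60 patients only a difference of about 58 to 77 points in TG percent change would be detected with 80% power. A non-significant result must not be read as evidence that the effect is the same in both groups.

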### **3.3.3 Sample Size Consideration**

Based upon prior clinical trial experience with volanesorsen, it is estimated that the standard deviation of the percent change in total fasting triglyceride is approximately 40%. With 20 volanesorsen patients and 20 placebo patients there would be approximately 80% power to detect a 40% difference in fasting triglyceride levels between treatment groups at an alpha level of 0.05, assuming 50% reduction in the volanesorsen treatment patients and 10% reduction in the placebo patients.

A sample size of 35 patients (20 active and 15 control) provides 92% power to detect a liver fat treatment difference of 4.7% based on a between patient standard deviation of 4% and a two-sided alpha of 0.05.

### **3.3.4 Planned Interim Analysis**

There is no interim analysis planned for the study.

### **3.3.5 Incomplete or Missing Data**

Patients with a missing primary endpoint will be excluded from primary efficacy analysis.

## **3.4 Secondary Analyses**

Secondary efficacy endpoints will be summarized by visit using descriptive statistics in FAS. Descriptive summary statistics refers to section 3.2.1. Visit includes baseline, and nominal visit as collected in CRF, or according to the visit window defined in [Appendix B](#) for MRI, HbA1c, and lipid endpoints

### **3.4.1 Secondary Endpoint Definitions**

The secondary endpoints include:

1. Percent Change from Baseline in hepatic steatosis (as assessed by hepatic fat fraction using magnetic resonance imaging [MRI])
2. Change from Baseline in hemoglobin A1c (HbA1c)
3. A composite endpoint at Month 6 for percent of patients who achieve
  - a.  $\geq 40\%$  reduction in fasting triglyceride, and
  - b.  $\geq 30\%$  reduction of hepatic fat fraction percent
4. Change in patient-reported outcomes (PRO):
  - o Patient-reported pain
  - o Patient-reported hunger
  - o QOL (EQ-5D, SF-36)

### ***3.4.2 Analysis of Secondary Endpoints***

#### ***3.4.2.1 Secondary Endpoint 1: Percent Change from Baseline in hepatic steatosis (as assessed by hepatic fat fraction using magnetic resonance imaging [MRI])***

Hepatic fat fraction (%), change from baseline, and percent change from baseline will be summarized by analysis visit using descriptive statistics in FAS. They will also be summarized separately by genetic mutation category: LMNA+PPARG, or neither. Descriptive summary statistics refers to section 3.2.1. Visit includes baseline and analysis visits according to the visit window defined in [Appendix B](#).

The percent change in Hepatic Fat Fraction (%) from Baseline to month 6 and month 12 at Randomized Treatment Period will be analyzed using the similar ANCOVA model as for the primary efficacy analysis model (ANCOVA).

A subgroup analysis of the ANCOVA will also be run for percent change in hepatic fat fraction in the group of genetically confirmed patients according to the University of Chicago data for patients who consented to genetic testing or historical data for patients who did not consent, and in patients with no mutation at month 6 and month 12 respectively.

#### ***3.4.2.2 Secondary Endpoint 2: Change from Baseline in HbA1c***

HbA1c (%), change from baseline, and percent change from baseline will be summarized by analysis visit using descriptive statistics in FAS. They will also be summarized separately by genetic mutation category: LMNA, PPARG, or neither. Descriptive summary statistics refers to section 3.2.1. Visit includes baseline and analysis visits according to the visit window defined in [Appendix B](#).

The change in HbA1c from Baseline to Randomized Treatment Period month 3, month 6, month 9 and month 12 will be analyzed using this similar ANCOVA model as for the primary efficacy analysis

A subgroup analysis of the ANCOVA will also be run for change in HbA1c from baseline in the group of genetically confirmed patients according to the University of Chicago data for patients who consented to genetic testing or historical data for patients who did not consent, and in patients with no mutation at month 3, month 6, month 9 and month 12 respectively.

**3.4.2.3 Secondary Endpoint 3: Proportion of patients who achieve a >=40% reduction in fasting triglyceride from Baseline and >=30% reduction of hepatic fat fraction percent from baseline at Month 6**

Frequency and proportion of patients who achieve a >=40% reduction in fasting triglyceride from baseline and >=30% reduction of hepatic fat fraction from baseline at Month 6 will be displayed.

**3.4.2.4 Secondary Endpoint 4: Patient reported pain and hunger**

No aggregated summary will be created.

**3.4.2.5 Secondary Endpoint 4: Change from baseline in QOL (EQ-5D, SF-36)**

No aggregated summary will be created.

**3.6 Pharmacokinetic and Anti-drug Antibody Analysis**

**3.6.1 Pharmacokinetic Analysis**

During the treatment period, blood samples for the determination of plasma volanesorsen concentrations will be collected from all patients prior to dosing, and at various times throughout the dosing and post-treatment follow-up period.

The sampling schedule is noted in the [Plasma PK Sampling Schedule](#) table below.

**Plasma PK Sampling Schedule**

Week	Wk 1	Wk 4	Wk 8	Wk 13	Wk 19	Wk 26	Wk 32	Wk 38	Wk 44	Wk 52
Study Day	1	22	50	85	127	176	218	260	302	358
Visit Window +/- Days	0	2	2	2	2	2	2	2	2	2
	Pre-dose									

Patients continuing to first year of OLE period

Week	Wk 56	Wk 60	Wk 65	Wk 71	Wk 78	Wk 84	Wk 90	Wk 96	Wk 104	Wk 110	Wk 117
Study Day	386	414	449	491	540	582	624	666	722	764	813
Visit Window +/- Days	2	2	2	2	2	2	2	2	2	7	7
	Pre-dose	Anytime	Anytime								

Patients continuing to second year of OLE period

Week	Wk 108	Wk 112	Wk 117	Wk 123	Wk 130	Wk 136	Wk 142	Wk 148	Wk 156	Wk 162	Wk 169
Study Day	750	778	813	855	904	946	988	1030	1086	1128	1177
Visit Window +/- Days	2	2	2	2	2	2	2	2	2	7	7
	Pre-dose	Anytime	Anytime								

Plasma concentrations of volanesorsen, along with the scheduled (nominal) and actual sampling times (i.e., time from SC dosing) will be listed (when applicable) for each patient, by treatment, patient ID, patient anti-drug antibody (ADA) status, and IM onset (if applicable) as defined in Section 3.6.2, and day. Plasma concentrations below the lower limit of quantification (LLOQ) will be presented as “0.00”.

For all patients who receive volanesorsen treatment, trough (pre-dose) and post-treatment volanesorsen plasma concentrations will be summarized by study day, with and without stratification by IM status (positive/negative or unknown), using descriptive statistics (n, mean, SD, SEM, %CV, geometric mean, geometric %CV, median, minimum, and maximum). For the purpose of calculating typical descriptive statistics for plasma concentrations, all below the lower limit of quantification (BLQ) values will be set to zero. Mean plasma concentrations that are BLQ will be presented as BLQ, and the SD and %CV will be reported as “NA” (not applicable). At the discretion of the pharmacokineticist and/or biostatistician, samples may be excluded from descriptive statistics if there are large deviations between scheduled and actual sampling times, or large deviations between actual dose and nominal dose.

Mean ( $\pm$ SD) plasma volanesorsen concentration-time plots with stratification by anti-drug antibody status will be generated on semi logarithmic scales.

